7 INVESTIGATIONAL PLAN

7.1 Overall Study Design and Plan

This open-label extension study will assess the long term safety and efficacy of SA treatment over a period of approximately 36 months, or until marketing approval or program termination by Ultragenyx. In Part I of the study, approximately 46 subjects will be enrolled following successful completion of the UX001-CL201 study. The Baseline visit will be conducted in conjunction with the UX001-CL201 Week 48 study visit to avoid treatment disruption. Enrollment will take place after all UX001-CL201 Week 48 study assessments have been completed and the investigator has determined the subject meets all eligibility criteria. Data collected at the UX001-CL201 Week 48 visit will serve as the Baseline data for Part I of this protocol. Following the signing of informed consent at the Baseline visit, each subject will be dispensed a 6-week supply of study drug. Throughout the Part I Treatment Period of the study, all subjects will continue to take four 500 mg SA-ER tablets orally three times per day (TID), in the morning, early evening, and at bedtime (qHS), for a total dose of 6g/day. The Part I Termination Visit will also serve as the Baseline Visit for Part II of the study.

Beginning with the Part II-Baseline Visit, all subjects currently enrolled in Part I will crossover to the SA-ER/SA-IR dosing regimen. Approximately 10 treatment naïve GNE Myopathy subjects will be enrolled into Part II of the study. The additional subjects will provide an assessment of SA-ER/SA-IR treatment in SA naïve subjects able to walk at least 200 meters (and < 80% predicted) in a screening 6 Minute Walk Test (6MWT). Throughout the 36-month Part II Treatment Period, all subjects will be administered 1.5g SA-ER and 1.5g SA-IR orally four times per day (QID), in the morning, afternoon, early evening, and qHS, for a total SA dose of 12g/day.

Part III of the study reduces the SA dose from 12g/day to 6g/day for subjects who did not show additional benefit at 12g/day at the interim analysis; however, treatment naïve subjects and a small subset of rollover subjects who showed a potential efficacy benefit will be invited to remain on the higher dose of 12g/day. Part III will assess the long-term safety and efficacy of 12g/day SA-ER/SA-IR treatment for the duration of the study for the subjects who stay on the higher dose in Part III and will provide additional information on the long-term safety and efficacy of 6g/day SA-ER for the remaining subjects.

Part IV was added to change the formulation from SA-IR to SA-ER. The SA-IR dose formulation has been removed based on data showing that by the 4th day of dosing in a nonclinical study conducted in dogs, AUC for free SA was similar between the immediate and extended release formulations. In addition, a review of population data for Month 12 of Part III in the current study confirmed that 12g/day SA-IR did not appear to provide any additional benefit compared with 6g/day SA-ER, although some individual patients may have improved. Therefore, no further SA-IR will be administered after the initiation of Part IV; patients currently on 12g/day may continue receiving the 12g/day dose, if desired, by taking SA-ER.

Evaluations of safety, changes in clinical endpoints such as muscle strength, mobility, and function, and changes in exploratory serum biomarkers will be performed according to the Schedule of Events specific to each phase of the study (Table 2.1 and Table 2.2). A Termination Visit will be conducted 4 weeks after subjects receive their last dose of study drug (last dose of study drug received at Month 36). For subjects who are eligible and choose to participate in the UX001-CL302 open-label extension study, the Month 36 Visit is considered the end of study visit and the Termination Visit is not required. Any subject who discontinues the current study early or is ineligible or decides not to participate in the UX001-CL302 extension study is required to have a Termination Visit 4 weeks after their last dose of study drug, as per Schedule of Events. Efficacy data analyses will be conducted at the end of the 36-month Treatment Period, although interim analyses may be performed at the discretion of Ultragenyx.

Safety will be monitored throughout the study based on physical examinations, clinical laboratory analyses, and reporting of adverse events (AEs) and SAEs. An independent Data Monitoring Committee (DMC) will review safety information periodically on an ad hoc basis as outlined in the DMC charter, which is maintained separately from this protocol.

7.2 Discussion of Study Design, Including Choice of Control Group

Part I of the study will focus on evaluating the long-term safety of 6g/day SA-ER treatment in GNE Myopathy subjects continuing SA-ER treatment as an extension of the 48-week, Phase 2 UX001-CL201 clinical study. Part I of the study will also explore long-term effects of SA-ER on clinical measures of muscle strength, mobility, function, disability and health-related quality of life. Exploratory evaluations of the effects of SA-ER on serum biomarkers will be performed in Part I of the study only.

Since Part I of the study is designed as an open-label extension designed to continue SA-ER treatment for subjects successfully completing the Phase 2 UX001-CL201 study, the study size and population are therefore restricted to said individuals. In UX001-CL201, safety and efficacy of SA-ER was examined in a randomized, double-blind study at two dose levels and compared to placebo treatment control. The current study design is not powered to assess statistically significant comparisons between treatment groups. Instead, the study population for Part I is intended to provide additional long-term safety data following maintenance treatment with 6g/day SA-ER. Since all subjects will receive the same treatment, randomization or blinding of study drug is not necessary.

The Week 24 interim data from the Phase 2 UX001-CL201 study implied a positive PD signal and acceptable safety profile suggesting the potential to optimize the therapeutic index by increasing SA exposure. Therefore, investigation into optimizing the risk-benefit profile of SA substrate replacement by examining higher SA doses is warranted. Part II of the study will assess the long-term safety and efficacy of an increased SA dose (total 12g/day) for up to 12 months. In this phase, SA treatment will be in the form of SA-ER tablets and immediate release capsules (SA-IR) to maximize absorption from the GI tract based on data obtained from nonclinical studies in canines. Continuing subjects will terminate Part I of the study

following approximately 12 weeks of treatment with 6g/day SA-ER and continue on to Part II of the study by crossing over to an increased daily SA dose of 12g/day. Since Part II of the study will be the first time GNE Myopathy subjects will be treated with the SA-ER/SA-IR investigational product, approximately 10 GNE Myopathy subjects will be enrolled to assess long-term safety and clinical efficacy of SA-ER/SA-IR in a treatment naïve population.

An interim analysis was conducted after 6 months of treatment with SA-ER/SA-IR; the results of this interim analysis have led to the establishment of Part III of the study. Part III will provide long-term safety and efficacy data on both 6 and 12g/day SA. This change is based on a review of individual subject data for the rollover subjects from the parent study UX001-CL201. The data analysis suggests that a small subset of subjects received an added benefit from the higher dose (defined as at least a 15% increase in either the UEC or LEC). The rollover subjects who met these criteria, along with the ongoing naïve subjects, had the option to remain on the 12g/day dose for the remainder of the study.

Part IV was added to change the formulation from SA-IR to SA-ER. The SA-IR dose formulation has been removed based on data showing that by the 4th day of dosing in a nonclinical study conducted in dogs, AUC for free SA was similar between the immediate and extended release formulations. In addition, a review of population data for Month 12 of Part III in the current study confirmed that 12g/day SA-IR did not appear to provide any additional benefit compared with 6g/day SA-ER, although some individual patients may have improved. Therefore, no further SA-IR will be administered after the initiation of Part IV; patients currently on 12g/day may continue receiving the 12g/day dose, if desired, by taking SA-ER.

Patients who elect to decrease from 12 g/day to 6 g/day may be allowed to do so upon Sponsor approval.

The 36-month treatment duration is intended to evaluate the long-term safety and efficacy of SA. While the lack of a control group may introduce difficulties in discerning natural disease progression from treatment effectiveness, due to the progressive debilitating nature of the disease, a placebo-controlled study of this duration is not feasible

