Ultragenyx is conducting this study (UX001-CL202) in four parts: Part I of the study will provide additional information on the long-term safety and efficacy of 6g/day SA-ER; Part II of the study will assess the long-term safety and efficacy of 12g/day SA (comprised of 1.5g of SA-ER and 1.5g of SA-IR treatment 4 times per day). Parts III and IV will provide long-term safety and efficacy data on both 6 and 12g/day SA (both SA-ER/SA-IR [Part III] and SA-ER [Part IV]). Part III was added based on a review of individual subject data for the rollover subjects from the parent study UX001-CL201 at Month 6. The data analysis suggested that a small subset of subjects received an added benefit from the higher dose (defined as at least a 15% increase in either the UEC or LEC). The rollover subjects who met these criteria, along with the ongoing naïve subjects, had the option to remain on the 12g/day dose for the remainder of the study. Part IV was added to change the formulation from SA-IR to SA-ER. The SA-IR dose formulation has been removed based on data showing that by the 4th day of dosing in a nonclinical study conducted in dogs, AUC for free SA was similar between the immediate

and extended release formulations. In addition, a review of population data for Month 12 of Part III in the current study confirmed that 12g/day SA-IR did not appear to provide any additional benefit compared with 6g/day SA-ER, although some individual patients may have improved. Therefore, no further SA-IR will be administered after the initiation of Part IV; patients currently on 12g/day may continue receiving the 12g/day dose, if desired, by taking SA-ER.

Patients who elect to decrease from 12g/day to 6g/day may be allowed to do so upon Sponsor approval.

OBJECTIVES:

The safety objectives of the study are to:

- Evaluate additional long-term safety of SA-ER treatment of GNE Myopathy subjects previously treated with SA-ER at dose of 6g/day (Part I)
- Evaluate the safety of 12g/day SA (delivered by 1.5g of SA-ER tablets and 1.5g of SA-IR capsules 4 times per day) in the treatment of GNE Myopathy subjects (Part II) over a 6 month treatment period.
- Evaluate the safety of SA treatment at both 6g/day and 12g/day (Part III [SA-ER/SA-IR] and Part IV [SA-ER]).

The clinical objectives of the study are to:

- Evaluate the long-term effect of SA treatment of GNE Myopathy subjects on muscle strength as measured by hand-held dynamometry (HHD)

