6 STUDY OBJECTIVES

The safety objectives of the study are to:

- Evaluate additional long-term safety of SA-ER treatment of GNE Myopathy subjects previously treated with SA-ER at dose of 6g/day (Part I)
- Evaluate the safety of 12g /day SA (delivered by 1.5g of SA-ER tablets and 1.5g of SA-IR capsules 4 times per day) in the treatment of GNE Myopathy subjects (Part II) over a 6 month treatment period
- Evaluate the safety of SA treatment at both 6g/day and 12 g/day (Part III [SA-ER/SA-IR] and Part IV [SA-ER]).

The clinical objectives of the study are to:

- Evaluate the long-term effect of SA treatment of GNE Myopathy subjects on muscle strength as measured by hand-held dynamometry (HHD)
- Evaluate the long-term effect of SA treatment of GNE Myopathy subjects on mobility, strength, and function using a series of physical performance measures
- Evaluate the long-term effect of SA treatment of GNE Myopathy subjects on functional disability using an interview-based questionnaire.

The exploratory objectives of the study are to:

- Evaluate the effect of SA-ER treatment on serum biomarkers of sialylation in GNE Myopathy subjects (Part I)
- Determine whether 12g/day SA-ER/SA-IR administered 1.5g/1.5g four times per day is superior to prior treatment with SA-ER in GNE Myopathy subjects (Part II)
 - Determine whether a subset of subjects has additional benefit on the higher dose treatment.

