7.5.2.1 Hand-held dynamometry

In Part I of the study, HHD testing will be performed at the Baseline and Part I Termination Visits, to assess muscle strength. For continuing subjects, the assessment at the Part I Termination Visit will serve as the baseline assessment for Part II of the study. HHD testing in Parts II, III, and IV of the study will be performed at Baseline (for treatment naïve subjects), Months 3, 6, 12, 18, 24, 30, 36 and Termination Visits. Formal training will be conducted with the licensed physical therapists administering the HHD testing to standardize technique and minimize variability. The maximum voluntary isometric contraction (MVIC) against a dynamometer will be used to measure strength in the following muscle groups: shoulder abductors, elbow flexors, elbow extensors, hip abductors, hip adductors, hip flexors, hip extensors, knee flexors and knee extensors. A hand dynamometer will be used to assess gross grip strength and a pinch dynamometer will be used to assess pinch strength. Each effort will last approximately three seconds with a slow build to a maximum voluntary force. Strength in the elbow flexors and elbow extensors will be measured with the subject lying in a supine position on an examination table. Strength in the hip extensors will be measured with the subject leaning over an examination table in a prone position. All other muscle groups will be tested with the subject in a sitting position. All measurements will be taken bilaterally. The administrator will attempt to obtain two force values within approximately 15% of each other for each muscle group. Testing positions may be altered at the discretion of the administrator to improve the reliability of the test. The total force (in kg) will be recorded at the time of test administration. The highest force value collected for each muscle group will be used for data analysis. The percent of predicted normal values will be calculated after the testing using published normative data ([Mathiowetz et al. 1985](#)); ([NIMS 1996](#)); ([Bohannon 1997b](#)); ([Bohannon et al. 2006](#)); ([Peters et al. 2011](#)).

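### The Month 6 rule for added benefit on 12 g/day has no comparator rate, and because Part III dose then follows it, later 12 g versus 6 g contrasts are confounded by selection

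*Protocol*

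**What the plan says.** An exploratory objective (Protocol Section 6) is to "Determine whether a subset of subjects has additional benefit on the higher dose treatment". Part III was added after a "review of individual subject data for the rollover subjects from the parent study UX001-CL201 at Month 6" (Synopsis). Section 7.2 gives the criterion: a small subset "received an added benefit from the higher dose (defined as at least a 15% increase in either the UEC or LEC"), where UEC and LEC are the upper and lower extremity strength composites. No confirmatory visit, named baseline or comparator rate accompanies it.

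The result then sets the dose. Part III "reduces the SA dose from 12g/day to 6g/day for subjects who did not show additional benefit at 12g/day at the interim analysis" (Section 7.1). Rollover subjects who met the rule, "along with the ongoing naïve subjects, had the option to remain on the 12g/day dose for the remainder of the study" (Section 7.2). Naïve subjects had to walk at least 200 m at entry (Section 7.3.1). Later movement is also by choice: "Patients who elect to decrease from 12 g/day to 6 g/day may be allowed to do so upon Sponsor approval" (Section 7.2).

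Section 7.1 reports that a review of population data for Month 12 of Part III "confirmed that 12g/day SA-IR did not appear to provide any additional benefit compared with 6g/day SA-ER", adding that some individuals may have improved. Section 7.6.1.1 names a treatment difference at Month 36 as the final estimate from the repeated measures model and leaves Part III and IV analyses to the SAP. The SAP supplied is written to Amendment 1, describes two parts (Section 1), does not contain the 15% rule, and allows several efficacy baselines (Section 6.5.8).

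**The concern.** A rise within one person is evidence of benefit from the higher dose only if the same rise is rarer without that dose. The protocol states no such rate, so the subset objective is not answered by the rule alone. Hand-held dynamometry depends on effort, treatment is open-label, and taking the better of two composites gives chance two opportunities.

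The second problem does not depend on how the rule is labelled. Rollover subjects kept on 12 g were chosen for a high Month 6 value relative to an earlier one, and those moved to 6 g were chosen for the lack of it. Naïve subjects on 12 g come from a different entry population. Comparing the two dose groups afterwards therefore mixes selection with dose. If the Month 36 treatment difference were read as 12 g versus 6 g, its sign could depend on the baseline chosen.

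**Working it through.** The plan gives no responder rate, composite error or power figure for the rule, so there is nothing of its own to reproduce.

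**Inputs from the documents.** Threshold 15% in either composite (Protocol Section 7.2); about 46 rollover subjects (Section 7.6.4), taken as an upper figure because the number reviewed at Month 6 is not given.

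**Assumptions.** Percent change is measured from the Part II baseline. Visit error is normal, independent between visits, with SD e (percent of baseline) in each composite. Errors in the two composites correlate at ρ = 0 to 0.5. True change is zero unless stated.

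**Step 1: chance of meeting the rule.** The SD of a change is e√2. With z = 15/(e√2), the single-composite chance is 1 − Φ(z), and the either-composite chance is 1 − Φ₂(z, z; ρ), where Φ₂ is the bivariate normal distribution function.

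| e | SD of change | z | One composite | Either (ρ = 0.5 to 0) | Of 46 |
|---|---|---|---|---|---|
| 3% | 4.24 | 3.54 | 0.02% | 0.04% | 0.02 |
| 4% | 5.66 | 2.65 | 0.4% | 0.8% | 0.4 |
| 6% | 8.49 | 1.77 | 3.9% | 6.9-7.6% | 3.2-3.5 |
| 8% | 11.31 | 1.33 | 9.2% | 15.6-17.6% | 7.2-8.1 |
| 10% | 14.14 | 1.06 | 14.4% | 23.4-26.8% | 10.8-12.3 |

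If true strength fell 3% over the six months (assumed), the numerator of z becomes 18. The counts fall to about 1.5 at e = 6% and 8-9 at e = 10%.

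**Step 2: what selection does at the next visit.** I simulated the Part II baseline, Month 6 and the next visit under noise only, with no dose effect, and applied the rule. In the selected subjects the better composite rises by a mean of 18-23% at Month 6 (e = 6-10%). It still stands 9-11% above the Part II baseline at the next visit. Half is kept because only the baseline error is shared.

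**Step 3: the false dose contrast.** The table gives retained minus stepped-down rollover subjects in UEC at the next visit, with ρ = 0 to 0.5.

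| e | From Part II baseline | From Month 6 | From an unused earlier visit |
|---|---|---|---|
| 6% | +4.9 to +7.0 | −4.9 to −7.1 | 0 |
| 8% | +5.8 to +8.3 | −5.9 to −8.3 | 0 |
| 10% | +7.0 to +9.8 | −7.1 to −9.8 | 0 |

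For example, at e = 8% and ρ = 0.5 the means are +7.0 (retained) and −1.3 (stepped down) from the Part II baseline, a gap of 8.3 points. From Month 6 they are −7.0 and +1.3, the same gap reversed. From a visit that played no part in selection the gap is zero within simulation error.

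**The case against.** The strongest reply is that the size is assumed. That stands. At 3% visit error noise yields essentially no responders, and the composites average two sides and sum four or five muscle groups (SAP Section 6.5.2), which reduces error. A reader might infer that the subset is noise; the documents show only that noise is not excluded.

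A reader might also take the measurement instruction "The administrator will attempt to obtain two force values within approximately 15% of each other for each muscle group" (Protocol Section 7.5.2.1) as showing that 15% is within error. It does not. It concerns two efforts on one muscle group at one sitting. If 95% of such pairs met the target, single-effort error would be about 15/(1.96√2) = 5.4%. Averaging 8 to 10 independent measures would then leave under 2%. Larger error would have to come from variation between visits, which is not reported.

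A third tempting reading is that the Month 12 statement compared the response-selected groups. The groups, periods and baseline are not given. Amendment 2, which added Part III, is dated 17 December 2014, and Amendment 3, which reports the review, 7 October 2015. That is 294 days, or 9.7 months, so nobody could have had 12 months of Part III. Month 12 is probably the visit on the common Part II-IV schedule (Table 2.2), and the sentence itself is hedged.

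It is also fair that the objective is exploratory, the wording is that the data suggest a subset, and the protocol admits the lack of a control group and of power. Section 7.6.1.1 plans a group-level comparison of the Month 6 change with the parent-study periods, and its whole-period strength analysis groups subjects by starting dose, not Part III dose. None of this supplies a comparator rate for the individual rule, and neither selection by response nor regression to the mean is mentioned.

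**Conclusion.** The point holds in two parts. First, the rule cannot by itself attribute a Month 6 rise to 12 g, because no rate under placebo, 3 g or 6 g is stated. This follows from the text. How much of the subset noise could explain is open, from none to about a quarter of 46 subjects over the errors considered. Second, Part III dose follows response, naïve status and choice, so a Part III/IV 12 g versus 6 g contrast is not a dose comparison whatever the error. The 5-10 point bias applies to rollover subjects at 6-10% error under the noise-only model. It leaves out the naïve subjects and real differences in progression, both of which add further non-comparability. No formal Part III dose test is written out, so the Month 36 estimate is at fault only if it is read that way.

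**What to change.** The changes concern analysis and interpretation only. Who takes which dose is untouched.

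1. Apply the identical rule to UX001-CL201 Weeks 0-24 by arm (placebo, 3 g, 6 g). Report those rates beside the Month 6 rate on 12 g, with confidence intervals for the differences that allow for the same subjects appearing in both studies. Note that the parent data were double-blind and these are open-label. Do not claim a subset benefit from the 12 g rate alone or from a bare numerical excess. With 46 subjects, assumed parent arms of 12-18, independent groups and one common true rate of 3-25%, the 12 g rate exceeds both the placebo and 6 g rates by chance about 28-38% of the time.
2. Assess persistence in retained rollover subjects at Months 12 and 18 against a visit not used in selection, for example UX001-CL201 Week 48. Use an earlier visit for those who went directly into Part II (SAP Figure 1 note), for whom Week 48 may be the Part II baseline. Do not use the Part II baseline or Month 6 as the sole reference.
3. Report retained rollover, stepped-down rollover and naïve subjects separately.
4. State that Part III/IV differences between 12 g and 6 g, including at Month 36, are not estimates of a dose effect.
5. State which groups, periods and baseline the Month 12 review compared, and soften the word *confirmed* if the groups were response-selected.

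The cost is SAP text and a few tables; the SAP (Section 5) already draws on parent-study data. No visits or subjects are added. The subset claim may become weaker, and a Week 48 reference adds the Part I interval to the change measured.
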